13.3. Criteria for Study Discontinuation

The principal investigator may discontinue part or all of the study in consultation with the sponsor if it is judged that it is not wise to continue the study in light of the results observed in the study. If the principal investigator prematurely terminates or suspends the clinical study without prior agreement with the sponsor, the principal investigator should immediately notify the sponsor and the IRB of the study site, and provide a detailed explanation of the early termination and discontinuation.

The IRB may decide to terminate early or discontinue the study if the ongoing study is conducted differently from the IRB's request or decisions, or if there is a significant unexpected risk to the subject. In this case, the IRB will immediately notify the head of the study site or the principal investigator of the decision and its reasons. In this case, the investigator will notify the sponsor immediately and submit a detailed explanation of the early termination and discontinuation.

The sponsor may discontinue part or all of the clinical study for safety or managerial reasons. If the study is terminated or discontinued early, the sponsor should promptly report such fact and reasons to the principal investigator and the Minister of Ministry of Food and Drug Safety. In the case of multicenter studies, principal investigators of other study sites conducting the study should also be notified of such fact and reasons in writing. In this case, the principal investigator will notify the IRB immediately and submit a detailed explanation of the early termination and discontinuation.

In the event of an early termination or discontinuation of the study, the principal investigator should immediately notify the subjects of such fact and ensure that appropriate measures and follow-up investigations are carried out. The principal investigator should organize the case record form,

Confidential Page 32 of 51

progress status and results of the study until the time of termination and provide them to the sponsor, and return the investigational products and all test-related data and products to the sponsor.

13.4. Handling of Protocol Deviations

The principal- and sub-investigators should be fully familiar with and thoroughly implement the protocol to avoid protocol deviations. If a deviation occurs during the study period, the investigator will document the deviation and take appropriate actions to correct the deviation.

As a rule, in the event of a critical deviation of protocol, the subject should be dropped from the analysis (excluded from the PP analysis), and the corresponding cases are as follows:

- 1) If the inclusion/exclusion criteria are not met
- 2 If the compliance of the investigational product is less than 80%
- If the patient has received medication or treatment that may have a significant impact on the outcome of the study

In addition, for minor deviations of protocol, which are judged to have no effect on the interpretation of the study results, the degree and reasons for deviation or delay should be accurately recorded and included in the PP analysis by comprehensively considering whether they had an impact on the study.

14. Statistical Analysis Method

14.1. Definition of Analysis Set

14.1.1. Analysis Set for Efficacy Assessment

Both Full Analysis Set (FAS) and Per-Protocol (PP) analyses are carried out for efficacy data, and as a rule, the results of the FAS will be interpreted as the main analysis results.

1) Full Analysis Set (FAS)

Among patients who received at least one dose of the investigational product, those who have not violated the inclusion/exclusion criteria and were subjected to at least one assessment of gallstone formation after randomization.

2) Per-Protocol (PP) Set

The PP Set is composed of subjects who have completed the study without a significant deviation of the protocol that could affect the efficacy of the FAS. The subjects who were terminated according to the early termination criteria of Section 13.2 are included in the PP Set. For subjects who are excluded from the PP Set for other significant deviations, the reasons will be clarified and documented before releasing blinding.

14.1.2. Analysis Set for Safety Assessment

It will consist of all subjects who have received the investigational product at least once among randomly assigned subjects.

14.2. General Principles of Result Analysis

All statistical analyses use SAS[®] 9.3 or higher and perform a two-sided test at a significance level of 5%.

The descriptive statistics (mean, standard deviation, minimum, median, and maximum) are provided for the continuous data (age, weight, height, BMI, etc.), and the frequency and proportion are provided for the categorical data (sex, etc.).

Confidential Page 33 of 51

If a missing value occurs due to a subject withdrawing before the end of the clinical study or a missing test at a certain point in time, etc., the analysis will be carried out without replacing the data unless otherwise specified and will be processed as missing (Observed Case).

14.3. Demographic Surveys and Other Baseline Characteristics

The demographics of all subjects included in the FAS are assessed for each treatment group. For the continuous data, descriptive statistics (mean, standard deviation, minimum, median, and maximum) will be provided, and the treatment groups should be compared using the ANOVA or Kruskal- Wallis test. Frequency and proportion are provided for the categorical data, and the treatment groups are compared using the chi-square test or the Fisher's exact test.

14.4. Efficacy Analysis

14.4.1. Primary Efficacy Endpoint

The primary efficacy endpoint is the percentage of patients with gallstone formation within 12 months after gastrectomy according to the assessment by an external investigator.

For the superiority testing of DWJ1319 over placebo on the incidence of gallstone formation, the sequential multiple testing will be performed for each treatment group according to the fixed sequence method.

- Step 1: Superiority testing for DWJ1319 600 mg compared with placebo (5% significance level)
- Step 2: Superiority testing for DWJ1319 300 mg compared with placebo (5% significance level)

As DWJ1319 600 mg is expected to be relatively more effective in preventing gallstones compared to DWJ1319 300 mg, the efficacy assessment of DWJ1319 600 mg versus placebo is given priority.

The step 2 test can be performed only if the result of step 1 test is statistically significant, and the conclusions about the superiority of DWJ1319 over placebo will be drawn based on the test result from each step. If the result of step 1 test is not statistically significant, the step 2 test will not be performed, and it will be concluded that both treatment groups of DWJ1319 have failed to demonstrate the superiority over placebo.

The test in each step will use the logistic regression model with the lymph node resection range and the method of gastrectomy as covariates and present the frequency and proportion along with 95% confidence interval of subjects who have formed gallstone within 12 months by treatment group.

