10.1. Study Design

This is a multicenter, randomized, double-blinded, placebo-controlled, phase 3 study. Subjects are patients who have been diagnosed with gastric cancer and underwent gastrectomy for treatment. Screening will be conducted on subjects who gave an informed consent to participate in the study. Subjects who meet the inclusion criteria and do not qualify as exclusion criteria will be randomly assigned to DWJ1319 300 mg (DWJ1319 300 mg, once a day), DWJ1319 600 mg (DWJ1319 300 mg, twice a day), or placebo (1: 1: 1). For randomization, stratified randomization using the study site, the lymph node resection range (D1+, D2), and the type of gastrectomy as the stratification factors will be performed and randomization will be performed within 2 weeks from gastrectomy. During the study period, the subjects will visit the study site at screening, randomization (Day 1) and at 3-month interval after the administration of investigational product (at 3, 6, 9, and 12 months) to undergo protocol-specified tests and procedures at each visit. However, any subject with formation of gallstone confirmed during the treatment period will terminate the study at the time of confirmation.

Visit 1	Visit 2	Visit 3	Visit 4	Visit 5	Visit 6
Until Week -2	Day 1	Month 3 ± 1 Week	Month 6 ± 1 Week	Month 9 ± 1 Week	Month 12 ± 1 Week
Screening	Randomizatio n	Treatment period			

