11.2.9. Assessment of Biliary Reflux Symptoms and Upper Gastrointestinal Endoscopy

The assessment of symptoms for a biliary reflux will be conducted at Visits 2 (baseline), 3, 4, 5 and 6, or at the time of early termination/withdrawal to determine the gallstone formation. The subjects completes a questionnaire (Appendix 2) in three areas including the frequency, strength, and the level of pain of the representative symptoms of biliary reflux (upper abdominal pain, heartburn, and nausea).

In addition, the investigator will perform an upper gastrointestinal endoscopy at Visits 3 and 6 to confirm the actual reflux of bile and record the results. There is no need for a separate endoscopy, but endoscopy results under routine clinical practices can be collected and used.

To diagnose bile reflux during the upper gastrointestinal endoscopy, the investigator will evaluate the status of bile reflux (Y/N) by observing the remnant stomach or the anastomotic area and determine it as bile if a yellow liquid is observed in the assessed area. If bile reflux is observed, gastritis is assessed as well according to the following criteria: ^{29),30)}

- 1) Grade 0: No flare on mucous membrane or the remnant stomach or anastomotic area.
- Grade 1: Mild redness is observed in the mucous membrane of the remnant stomach or anastomotic area.
- 3) Grade 2: A comb-shaped redness is observed on mucous membrane of the remnant stomach or anastomotic area.
- 4) Grade 3: Severe redness and edema are observed on mucous membrane of the remnant stomach or throughout the anastomotic area.

[figure not shown]

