14.4.2. Secondary Efficacy Endpoints

- 1) Proportion of patients with gallstone formation within 3, 6, 9, and 12 months after gastrectomy. The frequency and proportion of subjects with gallstone formation at each time point and the corresponding 95% confidence interval are provided for each treatment group. And the difference in the gallstone onset rate between each treatment group of DWJ1319 and the placebo is analyzed using a logistic regression model with the lymph node resection range and the type of gastrectomy as covariates.
- 2) Proportion of patients with gallstone formation within 3, 6, 9 months after gastrectomy according to the assessment by an external investigator

The frequency and proportion of subjects with gallstone formation at each time point and the corresponding 95% confidence interval are provided for each treatment group according to the

Confidential Page 34 of 51

assessment of outside researchers. And the difference in the gallstone onset rate between each treatment group of DWJ1319 and the placebo is analyzed using a logistic regression model with the lymph node resection range and the type of gastrectomy as covariates.

- 3) Proportion of patients with biliary sludge within 3, 6, 9, 12 months after gastrectomy. The frequency and proportion of subjects with the formation of biliary sludge at each time point and the corresponding 95% confidence interval are provided for each treatment group. And the difference in the biliary sludge onset rate between each treatment group of DWJ1319 and the placebo is analyzed using a logistic regression model with the lymph node resection range and the type of gastrectomy as covariates.
- 4) Time taken for gallstone formation

The period from the date of gastrectomy to the date of gallstone formation is calculated based on the following criteria.

Early termination due to gallstone formation within 12 months after gastrectomy or completion due to gallstone formation at 12 months will be treated as an incidence, and the period until the early termination or completion will be computed.

If gallstones are not formed until the completion of the clinical study, it will be treated as cut-off data, and the time to completion will be calculated. If the patient is withdrawn within 12 months after the gastrectomy, it will be treated as cut-off data and the time to dropout will be calculated.

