The time taken up to gallstone formation will be presented for each treatment group, and as for the time taken to gallstone formation, comparison between each treatment group of DWJ1319 and the placebo will be analyzed using the cox proportional hazards regression model with the lymph node resection range and gastrectomy as prognostic factors.

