14.4.3. Other Efficacy Endpoints

1) Changes in the bile reflux symptoms from baseline value (score for each area and the overall score) at 3, 6, 9, and 12 months

For scores of questionnaire on bile reflux symptoms, the score of each typical symptom (upper abdominal pain, heartburn, nausea) and the total score of symptoms will be presented in three categories which are frequency, intensity, and the level of distress.

Descriptive statistics (mean, standard deviation, minimum, median, and maximum) for changes in the bile reflux symptom score and changes compared to the baseline value at each time point are provided for each treatment group. And the difference in the changes in the bile reflux symptom score between each treatment group of DWJ1319 and the placebo is analyzed using the analysis of covariance with the lymph node resection range and the type of gastrectomy as covariates.

 Percentage of subjects who developed biliary reflux according to the upper gastrointestinal endoscopy at 3 and 12 months

The frequency and proportion of subjects with biliary reflux at each time point and the corresponding 95% confidence interval are provided for each treatment group. And the difference in the biliary reflux onset rate between each treatment group of DWJ1319 and the placebo is analyzed using a logistic regression model with the lymph node resection range and the type of gastrectomy as covariates.

Percentage of subjects with significant AST and ALT abnormalities at 6 and 12 months
 The frequency and percentage of subjects for whom the AST and ALT of the laboratory test were

Confidential Page 35 of 51

determined to be clinically significant abnormalities at the 6th and 12th month after gastrectomy were presented, and the difference between each dose of DWJ1319 versus placebo for the clinically significant abnormal percentage are analyzed using a logistic regression model with the lymph node resection range and type of gastrectomy as covariates.

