8.4.1 Primary Efficacy Analysis

The primary efficacy endpoint is the percentage of subjects with gallstone formation within 12 months of gastrectomy based on the external investigator's assessment.

For the superiority test of DWJ1319 over placebo on the incidence of gallstone formation, sequential multiple testing will be performed for each treatment group according to the fixed sequence method.

Step 1: Superiority testing for DWJ1319 600 mg compared with placebo (5% significance level)

Protocol No.: DW_UDCA005 English Translation Version

Step 2: Superiority testing for DWJ1319 300 mg compared with placebo (5% significance level)

As DWJ1319 600 mg is expected to be relatively more effective in preventing gallstones compared to DWJ1319 300 mg, the efficacy assessment of DWJ1319 600 mg versus placebo is given priority.

The step 2 test can be performed only if the result of the step 1 test is statistically significant, and conclusions about the superiority of DWJ1319 over placebo will be drawn based on the test result from each step. If the result of the step 1 test is not statistically significant, the step 2 test will not be performed, and it will be concluded that both treatment groups of DWJ1319 have failed to demonstrate superiority over placebo.

The frequency, percentage (%), and corresponding 95% confidence intervals are presented for the subjects with gallstone formation within 12 months by each treatment group. The comparison between each treatment group of DWJ1319 versus the placebo is analyzed using the Logistic Regression Model, with the lymph node resection range (D1+, D2) and the type of gastrectomy (Total gastrectomy, partial gastrectomy) as the covariates and the respective factors are defined as the following. The factors are defined as treatment group (DWJ1319 600 mg vs Placebo) for Step 1, treatment group (DWJ1319 300 mg vs Placebo) for Step 2, and treatment group (Placebo, DWJ1319 600 mg and DWJ1319 300 mg) for sensitivity analysis. Logistic Regression Model results are presented as odds ratios, corresponding 95% confidence intervals and two-sided p-values, and p-value is used for the final determination.

A summary of the data is presented in the following tables.

- T. Percentage of Subjects with Gallstone Formation within 12 month by the External Investigator's Assessment [DWJ1319 600mg vs Placebo] (FAS)

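### The reflux-symptom ANCOVA omits the baseline score and loses precision; separately, study site, a randomisation stratum, is left out of the logistic and Cox models, which makes those tests mildly conservative if sites differ.

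*Protocol*

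**What the plan says.** Protocol section 10.1 calls for "stratified randomization using the study site, the lymph node resection range (D1+, D2), and the type of gastrectomy as the stratification factors". Section 10.5.1 lists two levels for each surgical factor and has the blocked allocation done by study site. The synopsis gives 12 sites.

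The efficacy models keep two of these three factors:

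- Primary endpoint (14.4.1): "The test in each step will use the logistic regression model with the lymph node resection range and the method of gastrectomy as covariates".
- Secondary binary endpoints (14.4.2): "analyzed using a logistic regression model with the lymph node resection range and the type of gastrectomy as covariates".
- Time to gallstone formation (14.4.2): "cox proportional hazards regression model with the lymph node resection range and gastrectomy as prognostic factors".
- Reflux symptoms (14.4.3): the outcome is "Changes in the bile reflux symptoms from baseline value (score for each area and the overall score) at 3, 6, 9, and 12 months", and the difference between arms "is analyzed using the analysis of covariance with the lymph node resection range and the type of gastrectomy as covariates".

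Section 11.2.9 shows that a baseline reflux score exists: "The assessment of symptoms for a biliary reflux will be conducted at Visits 2 (baseline), 3, 4, 5 and 6".

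The covariates are therefore fixed in the protocol itself. The statistical analysis plan text in the same file repeats them: section 8.4.1 fits the primary model "with the lymph node resection range (D1+, D2) and the type of gastrectomy (Total gastrectomy, partial gastrectomy) as the covariates", and sections 8.4.2 and 8.4.3 use the same pair. Neither document gives a reason for dropping site or the baseline score.

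**The concern.** An analysis of covariance of a change from baseline normally carries the baseline value. Without it, the reflux analysis is an analysis of variance of change scores with two surgical factors. That costs precision whenever the regression of follow-up on baseline has a slope other than 1. It also lets a chance difference at Visit 2 feed into the estimated effect.

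For site, the allocation is balanced within site but the tests do not use that restriction. If gallstone rates differ between sites, the between-site variation that randomisation removed from the treatment comparison is still counted as error, so the test is conservative. Some variation is plausible because every site acquires its own ultrasound images, and for the secondary gallstone and sludge endpoints the site investigator also reads them. The primary test has only 80% planned power and acts as gatekeeper: failure at 600 mg stops the test of 300 mg. A few points of power at step 1 therefore bear on both dose claims.

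**Working it through.** **The plan's own figure.** Inputs from protocol section 8.3: 18% on placebo, 7% on each dose, two-sided 5%, 80% power.

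(1.96 + 0.842)² × (0.07 × 0.93 + 0.18 × 0.82) / 0.11² = 7.851 × 0.2127 / 0.0121 = 138.0 per group. Then 138 / 0.8 = 172.5, rounded up to 173, and 3 × 173 = 519. The figures reproduce and do not depend on the covariates.

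**Reflux ANCOVA.** Let σ² be the variance at both times (equal, assumed) and ρ the correlation of baseline with follow-up (not in the documents; assumed 0.2 to 0.8).

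- Variance of a change score: 2σ²(1 − ρ).
- Residual variance after adjusting for baseline: σ²(1 − ρ²).
- Ratio, adjusted to unadjusted: (1 + ρ)/2. The planned standard error is thus √(2/(1 + ρ)) times the adjusted one.

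| ρ (assumed) | Planned SE / adjusted SE | Extra subjects for equal precision |
|---|---|---|
| 0.2 | 1.29 | 67% |
| 0.5 | 1.15 | 33% |
| 0.8 | 1.05 | 11% |

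With unequal SDs σ₀ (baseline) and σ₁ (follow-up), the change-score variance exceeds the adjusted one by (σ₀ − ρσ₁)², which is never negative. The size of the loss depends on the assumption; its direction does not.

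For chance imbalance: if the arms differ by d at Visit 2, the expected difference in change without any drug effect is −(1 − ρ)d under equal variances. At ρ = 0.5 that is half of d.

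**Site in the primary logistic model.** Simulation of the step 1 comparison: 138 per arm, 12 equal sites balanced within site, 18% against 7%, the two planned covariates in the model (given no effect on outcome), fitted with and without site terms. There were 2,000 trials per setting, and 4,000 under the null at 18% in both arms. The between-site SD of the log-odds is not in the documents and is assumed.

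| Site SD | Median log OR, without → with site | Median SE, without → with | Power, without → with | Type I error, without → with |
|---|---|---|---|---|
| 0 | −1.121 → −1.169 | 0.409 → 0.420 | 81.0% → 82.2% | 5.7% → 6.2% |
| 0.5 | −1.091 → −1.166 | 0.409 → 0.425 | 80.8% → 82.9% | 4.6% → 5.2% |
| 1.0 | −1.095 → −1.261 | 0.410 → 0.444 | 79.3% → 83.6% | 3.5% → 5.2% |

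- The standard error rises when site is added, by 3% (0.420/0.409), 4% (0.425/0.409) and 8% (0.444/0.410). It was larger with site in every simulated trial. The odds ratio is non-collapsible, so adjustment moves the estimate and its standard error up together.
- The ratio of median estimate to median SE improves: 1.091/0.409 = 2.67 to 1.166/0.425 = 2.74 at SD 0.5, and 1.095/0.410 = 2.67 to 1.261/0.444 = 2.84 at SD 1.0.
- The SD 0 row is a caution. With no site differences, the site terms still shift the estimate by about 0.05 and type I error is 6.2%. The 1-point power gain in that row is therefore not a real gain.

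**Without site fixed effects.** A second simulation (12 unequal sites balanced within site, 138 per arm, 4,000 trials per setting) compared the unstratified odds ratio with a site-stratified Mantel-Haenszel test, neither adjusted for the surgical factors. At site SD 0.5, 0.8 and 1.0, type I error was 4.6%, 3.6% and 3.4% without site and 5.1%, 4.4% and 4.8% with it. Power was 80%, 80% and 79% without and 82%, 82% and 83% with.

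**Sparsity.** Expected events in the step 1 comparison: 138 × (0.18 + 0.07) = 34.5, or 34.5/12 = 2.9 per site. With a drug effect, 0.5 to 2.1 sites per simulated trial had no event.

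**The case against.** The strongest case is that leaving out site is a sound choice. About 35 events over 12 sites cannot support 12 site parameters, and the SD 0 row shows that fitting them can make the Wald test liberal. The gain is small: power without site stays at 79% to 81%, essentially the planned 80%. At site SD 0.5 the 4.6% type I error lies within about 1.2 Monte Carlo standard errors of 5% (√(0.05 × 0.95/4000) = 0.34%), so a clear shortfall needs a larger assumed SD. The error is conservative and creates no false-positive risk. All of this stands. It rules out site fixed effects, but not a Cochran-Mantel-Haenszel or conditional analysis, which estimates no site parameters.

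A reader might also infer that dropping site makes the confidence interval of the primary odds ratio too wide. The documents and the calculation do not support that: adding site raises the standard error of the log odds ratio. The same non-collapsibility applies to the Cox model, which was not simulated.

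Nor can one say that primary results must differ by site because site staff read the scans. Protocol sections 11.2.8 and 14.4.1 rest the primary endpoint on three external readers who see images from all sites in random order. Site influence is reduced rather than removed: sites acquire the images, and section 6.1.1 of the analysis plan counts early terminations for site-confirmed stones as events whatever the external readers say.

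On the reflux part, it is fair to say that this is one of the other (exploratory) endpoints, outside the fixed-sequence test. That limits its weight but does not justify the omission.

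**Conclusion.** Both omissions are real, and both are modest.

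The reflux part is clear-cut. A baseline score collected at Visit 2 is left out of an analysis of change, and the standard error is about 5% to 29% larger than needed for ρ from 0.8 down to 0.2. That range rests on equal variances and an assumed correlation. No primary or secondary claim depends on it.

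The site part is conditional. If sites differ, the odds ratio is pulled towards 1, type I error falls to about 4.6% at site SD 0.5 and 3.5% at SD 1.0, and about 2 to 4 points of power are lost. If they do not differ, nothing material is lost. The site SDs are assumptions. The primary test remains valid and close to its planned power.

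**What to change.** 1. **Reflux symptoms.** Add to the ANCOVA in protocol 14.4.3 and analysis plan 8.4.3 the Visit 2 score of the same item, domain or total as a covariate. Cost: one model term. Subjects without a Visit 2 score already have no change score, so none are lost.

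2. **Site.** For the primary and secondary binary endpoints, specify a site-stratified Cochran-Mantel-Haenszel test, or logistic regression conditional on site that keeps lymph node range and gastrectomy type as covariates. For time to gallstone formation, stratify the Cox model by site (`STRATA site`). Do not fit 12 site fixed effects. If the present primary model is kept, state why site is left out and prespecify the stratified analysis as a sensitivity analysis. Cost: a sentence and a line of code per model, settled before unblinding. Sites with no events contribute no information, which will matter more at the early time points, where cumulative events can only be fewer. The conditional logistic version was not simulated here and should be checked before it is made primary.
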